### 6.1.3. Laboratory Data

Laboratory data will be listed and summarized by treatment in accordance with the sponsor reporting standards.

#### 6.1.4. Vital Signs

Supine blood pressure, pulse rate, temperature and respiratory rate will be measured at times specified in the SoA given in the protocol.

The following vital signs endpoints will be determined and summarized for each treatment group:

 Actual values, change from baseline in supine blood pressure and pulse rate over all measurements taken postdose.

The increase from baseline will be calculated by subtracting the baseline value from each postdose measurement to give the change from baseline for each participant. The maximum of these values over the duration of dosing will be reported as maximum increase from baseline, except where a participant does not show an increase. In such an instance, the minimum decrease will be reported.

Similarly, decrease from baseline will be calculated by subtracting each post-dose measurement from individual participant's baseline value. Maximum decrease from baseline will be reported as the minimum value of the changes from baseline. In cases where a participant does not show a decrease, the minimum increase will be reported.

Maximum absolute values and changes from baseline for vital signs will also be tabulated by treatment using categories as defined in Appendix 1.

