4.1.1. Part A: Single Ascending Doses in Healthy Participants

Approximately 35 healthy adult participants will be enrolled at 1 or more sites into the proposed cohorts listed below. Participants may only participate in 1 cohort.

Participants in the single dose cohorts will be randomized sequentially as follows:

- Cohort 1 (n=4): PF-07261271 mg (n=2) or placebo (n=2), IV;
- Cohort 2 (n= 4): PF-07261271 mg (n=2) or placebo (n=2), IV;
- Cohort 3 (n=6): PF-07261271 mg (n=4) or placebo (n=2), IV;
- Cohort 4 (n=8): PF-07261271 mg (n=6) or placebo (n=2), IV.

An optional dose cohort may be added based on emerging PK and safety/tolerability data. This cohort (Cohort 7) will be randomized as follows:

Cohort 7 (n=8): single PF-07261271 dose (n=6) or placebo (n=2), IV.

An optional cohort of Japanese participants may be included in the study at the discretion of the sponsor. This cohort (Cohort 8) will be randomized as follows:

Cohort 8 (n=5): PF-07261271 at dose tested in the sequence above that is determined
to be safe and well-tolerated based on emerging data from preceding cohorts (n=4) or
placebo (n=1), IV or SC.

Within approximately 35 days of successful completion of the screening process, eligible participants will be randomized to receive a single IV infusion of PF-07261271 or placebo. In order to mitigate any unanticipated acute safety risks within the SAD cohorts, sentinel dosing will be implemented in all SAD cohorts (ie, cohorts where the dose being tested is the highest administered in the study to date). For sentinel dosing, the first 2 participants (1 active:1 placebo) will be dosed and monitored for at least 24 hours to assess safety and tolerability prior to dosing the remaining participants in the cohort. If the dose level for the first 2 sentinel participants is determined to have an acceptable safety and tolerability profile, as judged by the investigator, the remaining participants within the cohort will be dosed.

Single dose cohorts will be enrolled sequentially in a dose escalating fashion starting from the lowest proposed dose (mg).

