# 3. ENDPOINTS AND BASELINE VARIABLES: DEFINITIONS AND CONVENTIONS

#### 3.1. Primary Endpoint(s): Safety Endpoints

The primary endpoints include:

- Incidence and severity of TEAEs, SAEs.
- Change from baseline in vital signs (BP, PR, and temperature measurements).
- Change from baseline in clinical laboratory values (chemistry and hematology including coagulation panel).

Change from baseline in ECG parameters (heart rate, QT, QTc, PR, and QRS intervals).

The following data are considered in standard safety summaries (see protocol for collection days, baseline assessment, and list of parameters):

- AEs;
- Safety laboratory tests;
- Vital signs (BP, PR, and temperature measurements);
- ECG.

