#### 6.1.5. Electrocardiograms

Changes from baseline for the ECG parameters HR, QT interval, QTc interval, PR interval, and QRS intervals will be summarized by treatment and time. The frequency of uncorrected QT values above 500 ms will be tabulated.

The maximum absolute value (post-dose) and the maximum increase from baseline for QTcF, QT, heart rate, PR and QRS, will be determined over all measurements taken postdose and reported.

The increase from baseline will be calculated by first subtracting each post-dose measurement from individual participant's baseline to give the change from baseline.

The number (%) of participants with maximum postdose QTcF values and maximum increases from baseline in the following categories will be tabulated by treatment:

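### SAP 6.1.4 gives two conflicting windows for the maximum vital-sign increase, and the undefined dosing window does not fit a single-infusion Part A

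*SAP*

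**What the plan says.** Change from baseline in vital signs is among the primary safety endpoints in SAP 3.1: "Change from baseline in vital signs (BP, PR, and temperature measurements".

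SAP 6.1.4 then describes the summaries in several steps, and they do not share one window:

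- The endpoint bullet reads "Actual values, change from baseline in supine blood pressure and pulse rate over all measurements taken postdose".
- The derivation starts from the same full set: "The increase from baseline will be calculated by subtracting the baseline value from each postdose measurement".
- The next sentence narrows it: "The maximum of these values over the duration of dosing will be reported as maximum increase from baseline".
- The decrease carries no dosing window: "Maximum decrease from baseline will be reported as the minimum value of the changes from baseline".
- The closing sentence, which sends maximum values and changes to the Appendix 1 categories, names no window.

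For the corresponding ECG quantities, SAP 6.1.5 says that the maximum value and maximum increase "will be determined over all measurements taken postdose and reported".

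On dosing, Protocol 4.1.1 says that Part A participants "will be randomized to receive a single IV infusion of PF-07261271 or placebo". The optional Japanese cohort may be dosed IV or SC.

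**The concern.** The narrowing sentence is the only one that tells a programmer how to derive the maximum increase, and its window is tied to a term that neither document defines. In a study with daily dosing the phrase would do little harm. Here Part A has one infusion and Part B has two doses, while blood pressure and pulse are followed for more than a year because the antibody was engineered for a long half-life.

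Two programmers working from this SAP could produce different maximum-increase tables. Under the literal reading, rises and falls in the same vital-sign table would cover different periods. A rise of at least 30 mm Hg systolic first seen at, say, Day 61 would not count in the maximum-increase category, while a fall of the same size on that day would count in the decrease category. The table would then tend to under-report rises relative to falls, and it would not line up with the ECG maxima.

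**Working it through.** The documents give no figure to reproduce: the study is descriptive, and its sample size is not based on statistical considerations. The check is a count of scheduled postdose blood pressure and pulse readings under each possible window.

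**Inputs (Protocol 1.3, Schedule of Activities)**

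- Part A, Table 1: 5 postdose readings (end of infusion; one at 4 h or 8 h, where column alignment is lost; 24 h; 96 h; Day 15).
- Part A, Table 2: 8 readings (Days 32, 46, 61, 91, 181, 271, 361, 451). Total 5 + 8 = 13.
- Part B, Table 3: 6 postdose readings (1 h; one at 4 h or 8 h; 24 h; 96 h; Day 8; Day 15).
- Part B, Table 4: 5 readings (Day 29 predose, 1 h, one at 4 h or 8 h, and 24 h; then Day 36). Time 0 of the second dose is on Day 29.
- Part B, Table 5: 8 readings (Days 51, 66, 81, 111, 201, 291, 381, 471). Total 6 + 5 + 8 = 19.
- Infusion length: the planned length is blacked out. Protocol 7.1.6 caps an interrupted infusion at 3 hours in total, so a 4 h or 8 h reading falls outside it.

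**Readings kept under each window**

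| Window | Kept | Left out |
|---|---|---|
| Part A, infusion only | at most 1 of 13 | 12/13 = 92% |
| Part A, Day 1 only | 2 of 13 | 11/13 = 85% |
| Part B, first dose to second dose | 6 + 1 = 7 of 19 | 12/19 = 63% |
| Part B, through the end of Day 29 | 6 + 3 = 9 of 19 | 10/19 = 53% |
| Either part, all postdose | all | 0 |

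Protocol 4.1.1 allows an earlier final visit than Day 451. If Part A ended at Day 271, the total would be 5 + 6 = 11, and the infusion window would leave out 10/11 = 91%. The conclusion does not depend on the exact count.

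**What is exposed.** The maximum increase enters Appendix 1 in two places: systolic increase of at least 30 mm Hg and diastolic increase of at least 20 mm Hg. Pulse has no increase-from-baseline category, so for pulse only the reported maximum increase is at stake.

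**Effect on flag counts (illustration only).** Assume independent readings, each with probability p of passing a threshold. The chance of at least one flag in k readings is 1 − (1 − p)^k.

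| p (assumed) | k = 1 | k = 13 |
|---|---|---|
| 1% | 1% | 1 − 0.99^13 = 12% |
| 2% | 2% | 1 − 0.98^13 = 23% |
| 5% | 5% | 1 − 0.95^13 = 49% |

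The direction is certain: fewer readings give fewer flags. The size is not, because readings from one person share a baseline and the documents give no variability.

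**The case against.** The strongest reply is that the exclusion is inferred and not stated. The values whose maximum is taken are the changes computed from each postdose measurement, and the bullet above sets the endpoint over all of them. The nearest related term in the SAP, the effective duration of treatment in 3.1.1, is applied to adverse events up to the last follow-up date. The intended window may well be all postdose readings. This has force, but it does not settle the matter: the adverse-event term is a different phrase in a different section and does not define the dosing window in 6.1.4.

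Three stronger conclusions are tempting and should not be drawn.

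- A reader might infer that the SAP leaves nearly all postdose readings out of the primary vital-sign summary. It does not. The change-from-baseline summary has no dosing window, and the maximum increase is one derived statistic in a study with no hypothesis test.
- A reader might infer that all the Appendix 1 vital-sign categories are affected. The decrease criteria, the low systolic and diastolic limits and the pulse limits carry no dosing window. Appendix 1 also requires measurements meeting its criteria to be listed in the study report. SAP 6.1 provides participant listings and a description of blood pressure and pulse abnormalities of potential concern. A late rise would therefore still be visible individually.
- A reader might infer a definite loss of ability to detect a drug effect. Any such figure needs a standard deviation, an effect size and a time course that the documents do not supply. Part of the gap between 1 and 13 readings is also noise, since a maximum over more readings crosses a threshold more often even with no drug effect.

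All three limits stand. What remains is the contradiction within 6.1.4.

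**Conclusion.** The concern holds as an internal inconsistency in SAP 6.1.4. The endpoint bullet and the maximum-increase sentence give different windows, and the second rests on an undefined term. Followed literally, the rule would keep at most about 1 of 13 scheduled postdose readings in Part A and about 7 of 19 in Part B. The consequence is confined to the per-participant maximum increase and the two Appendix 1 blood-pressure increase categories, which would no longer match the maximum decrease or the ECG maxima in period covered.

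The counts assume the full scheduled follow-up and the schedule as it can be read from damaged tables. The Part B figure further assumes that dosing ends at the second dose on Day 29; optional Cohort 6 could follow another regimen. No probability of missed rises is claimed. This is a limited wording defect, but it sits in a derivation rule for a primary safety variable and is worth correcting before the tables are programmed.

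**What to change.** In SAP 6.1.4, delete the dosing-window phrase from the maximum-increase sentence and put in its place the wording already used in the bullet of that section and in 6.1.5, so that the maximum is taken over all measurements taken postdose. State that the same window applies to the maximum decrease and to the Appendix 1 vital-sign categories.

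The SAP's existing wording is enough. Whether unscheduled readings should enter the maxima is a separate choice, and this correction need not decide it.

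The cost is one phrase and one clarifying sentence in the SAP. No new data are needed. Protocol 9.3.1 contains no dosing window for vital signs, so its text does not need to change.

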#### 6.1.5. Electrocardiograms

Changes from baseline for the ECG parameters HR, QT interval, QTc interval, PR interval, and QRS intervals will be summarized by treatment and time. The frequency of uncorrected QT values above 500 ms will be tabulated.

The maximum absolute value (post-dose) and the maximum increase from baseline for QTcF, QT, heart rate, PR and QRS, will be determined over all measurements taken postdose and reported.

The increase from baseline will be calculated by first subtracting each post-dose measurement from individual participant's baseline to give the change from baseline.

The number (%) of participants with maximum postdose QTcF values and maximum increases from baseline in the following categories will be tabulated by treatment:

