10.8. Appendix 8: ECG Findings of Potential Clinical Concern

ECG Findings That May Qualify as AEs

- Marked sinus bradycardia (rate <40 bpm) lasting minutes.
- New PR interval prolongation >280 ms.
- New prolongation of QTcF to >480 ms (absolute) or by ≥60 ms from baseline.
- New-onset atrial flutter or fibrillation, with controlled ventricular response rate: ie, rate <120 bpm.
- New-onset type I second-degree (Wenckebach) AV block of >30 seconds' duration.
- Frequent PVCs, triplets, or short intervals (<30 seconds) of consecutive ventricular complexes.

ECG Findings That May Qualify as SAEs

- QTcF prolongation >500 ms.
- New ST-T changes suggestive of myocardial ischemia.
- New-onset LBBB (QRS complex>120 ms).
- New-onset right bundle branch block (QRS complex>120 ms).
- Symptomatic bradycardia.
- Asystole:
 - In awake, symptom-free participants in sinus rhythm, with documented periods of asystole ≥3.0 seconds or any escape rate <40 bpm, or with an escape rhythm that is below the AV node.
 - In awake, symptom-free participants with atrial fibrillation and bradycardia with 1 or more pauses of at least 5 seconds or longer.
 - Atrial flutter or fibrillation, with rapid ventricular response rate: rapid = rate
 >120 bpm.
- Sustained supraventricular tachycardia (rate >120 bpm) ("sustained" = short duration with relevant symptoms or lasting >1 minute).
- Ventricular rhythms >30 seconds' duration, including idioventricular rhythm (HR <40 bpm), accelerated idioventricular rhythm (HR >40 bpm to <100 bpm), and

monomorphic/polymorphic ventricular tachycardia (HR >100 bpm [such as torsades de pointes]).

- Type II second-degree (Mobitz II) AV block.
- Complete (third-degree) heart block.

ECG Findings That Qualify as SAEs

- Change in pattern suggestive of new myocardial infarction.
- Sustained ventricular tachyarrhythmias (>30 seconds' duration).
- Second- or third-degree AV block requiring pacemaker placement.
- Asystolic pauses requiring pacemaker placement.
- Atrial flutter or fibrillation with rapid ventricular response requiring cardioversion.
- Ventricular fibrillation/flutter.
- At the discretion of the investigator, any arrhythmia classified as an adverse experience.

The enumerated list of major events of potential clinical concern are recommended as "alerts" or notifications from the core ECG laboratory to the investigator and Pfizer study team, and not to be considered as all-inclusive of what to be reported as AEs/SAEs.

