#### 5.2.1. Analyses for Continuous Endpoints

For continuous variables, the data will be summarized using the number of participants, mean, median, standard deviation, minimum, and maximum in accordance with current Pfizer's data and reporting standards. For appropriate PK parameters, geometric mean and geometric coefficient of variation (geocv%) will also be summarized.

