#### Safety QTcF Assessment

Degree of Prolongation	Mild (ms)	Moderate (ms)	Severe (ms)
Absolute value	>450-480	>480-500	>500
Increase from baseline		30-60	>60

In addition, the number of participants with uncorrected QT values >500 ms will be summarized.

If more than 1 ECG is collected at a nominal time after dose administration (for example, triplicate ECGs), the mean of the replicate measurements will be used to represent a single observation at that time point. If any of the 3 individual ECG tracings has a QTcF value >500 ms, but the mean of the triplicates is not >500 ms, the data from the participant's individual tracing will be described in a safety section of the CSR in order to place the >500 ms value in appropriate clinical context. However, values from individual tracings within triplicate measurements that are >500 ms will not be included in the categorical analysis unless the average from the triplicate measurements is also >500 ms. Changes from baseline will be defined as the change between the postdose QTcF value and the average of the predose triplicate values on Day 1.

In addition, an attempt will be made to explore and characterize the relationship between serum concentration and QT interval length using a PK/PD modeling approach. If a PK/PD relationship is found, the impact of participant factors (covariates) on the relationship will be examined.

In addition, PR and QRS maximum values and maximum increases from baseline will also be tabulated by treatment using categories as defined in Appendix 1.

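### SAP 6.1.5 gives participant-level ECG heart-rate extremes in the upward direction only, and Appendix 1 has no ECG heart-rate class, unlike pulse rate: a minor reporting gap

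*SAP*

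**What the plan says.** ECG heart rate is part of a named primary endpoint. SAP 3.1 lists "Change from baseline in ECG parameters (heart rate, QT, QTc, PR, and QRS intervals".

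SAP 6.1.5 plans three kinds of ECG summary:

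- **By time.** "Changes from baseline for the ECG parameters HR, QT interval, QTc interval, PR interval, and QRS intervals will be summarized by treatment and time". Under SAP 5.2.1, continuous summaries carry the "mean, median, standard deviation, minimum, and maximum in accordance with current Pfizer's data and reporting standards".
- **Per-participant extremes.** "The maximum absolute value (post-dose) and the maximum increase from baseline for QTcF, QT, heart rate, PR and QRS" are to be determined over all postdose measurements.
- **Categories.** QTcF classes and counts of uncorrected QT above 500 ms; in addition, "PR and QRS maximum values and maximum increases from baseline will also be tabulated by treatment using categories as defined in Appendix 1". Heart rate is not included.

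SAP Appendix 1 has ECG classes for QTcF, PR and QRS only. For supine pulse rate it has classes for a minimum below 40 bpm and a maximum above 120 bpm.

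For vital signs, SAP 6.1.4 derives both directions. After defining the increase it continues: "Similarly, decrease from baseline will be calculated by subtracting each post-dose measurement from individual participant's baseline value". It then reports a maximum decrease.

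SAP 6.1.5 defines the ECG increase in these words: "The increase from baseline will be calculated by first subtracting each post-dose measurement from individual participant's baseline to give the change from baseline".

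Protocol Appendix 8 includes "Marked sinus bradycardia (rate <40 bpm) lasting minutes" among the ECG findings that may qualify as AEs, and symptomatic bradycardia among those that may qualify as SAEs.

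**The concern.** Heart rate sits in a list with QTcF, QT, PR and QRS. For those intervals the classes in the SAP and the findings in Protocol Appendix 8 concern prolongation, so an upper extreme is the natural summary. Heart rate is different: the protocol names low rates as findings of concern, and the SAP treats pulse rate in both directions. It gives no reason for treating the ECG rate in one direction only.

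At stake is how easily a reader of the study report could see a transient fall in one participant. Cohorts have 2 to 6 active participants, so per-participant extremes and counts are the tables most likely to be read for isolated events. For a fall in ECG heart rate they are not specified.

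**Working it through.** There is no sample size, power or other stated figure to reproduce. The check sets the rules side by side and then applies them to assumed heart rates.

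**Step 1: coverage as written**

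| Output | Pulse rate (SAP 6.1.4, Appendix 1) | ECG heart rate (SAP 6.1.5, Appendix 1) |
|---|---|---|
| Largest increase per participant | Yes | Yes |
| Largest decrease per participant | Yes | No |
| Low class, number (%) | Minimum <40 bpm | None |
| High class, number (%) | Maximum >120 bpm | None |
| By-time change, with minimum and maximum | Yes | Yes |

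**Step 2: per-participant extremes**

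Three assumed participants, each with baseline 65 bpm and five postdose values. The values are illustrative and not from the documents. Increase = postdose − baseline, the sense used in SAP 6.1.4.

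| Pattern | Postdose (bpm) | Maximum value | Maximum increase | Minimum value (not specified) | Largest fall (not specified) |
|---|---|---|---|---|---|
| Transient fall | 66, 38, 52, 64, 67 | 67 | 67 − 65 = +2 | 38 | 65 − 38 = 27 |
| No effect | 66, 64, 65, 63, 67 | 67 | 67 − 65 = +2 | 63 | 65 − 63 = 2 |
| Sustained fall | 55, 50, 48, 52, 54 | 55 | 55 − 65 = −10 | 48 | 65 − 48 = 17 |

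The first two rows cannot be told apart on the two specified extremes. The third can, because a sustained fall pulls both down. SAP 6.1.5 does not say what to report when a participant shows no increase; SAP 6.1.4 does.

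**Step 3: by-time summary**

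Take six active participants, one with the transient fall and five with no effect. At the second time point the changes are −27 once and −1 five times. Mean = (−27 − 5)/6 = −5.33; minimum = −27. The fall is visible here.

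This summary has limits. SAP 6.1.5 specifies it for changes, so the rate of 38 bpm itself is not shown. It does not count participants. The minima at different times may belong to different people.

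**Step 4: the subtraction as written**

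Taken literally, the ECG sentence computes baseline − postdose. For the transient fall this gives −1, 27, 13, 1 and −2, so the largest value is +27: a fall labelled as an increase. The +2 in Step 2 therefore rests on reading the sentence in the sense of SAP 6.1.4. Neither reading reports the fall correctly. The sentence is not limited to heart rate, so the order matters for all five ECG parameters.

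**The case against.** The strongest case against is that the signal is not lost. The by-time minimum change is specified, and with 2 to 6 active participants per cohort that minimum is one person's value. SAP 6.1 promises participant listings for the safety endpoints, ECG heart rate included. It also says ECG abnormalities of potential clinical concern will be described, with no limit on direction. Protocol 7.1.2 requires new clinically relevant ECG findings to be reported as AEs. The pulse-rate tables cover much of the same physiology. The study is descriptive, and no decision rule depends on the missing table. All of this stands.

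A reader might infer from the one-sided wording that a fall in heart rate cannot appear in any ECG summary. The documents do not support that: Step 3 shows it as a by-time minimum, and a sustained fall also lowers the specified extremes.

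A reader might also infer that pulse rate cannot substitute because ECGs are scheduled at times without vital signs. The Protocol 1.3 tables seem to show more ECG times, but their columns could not be read reliably, so no particular gap is claimed. What remains is that pulse rate is a separate measurement and the SAP does not say it stands in for ECG heart rate.

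Finally, the Appendix 8 bradycardia finding requires a duration of minutes, while Protocol 8.3.3 specifies a 10-second rhythm strip. An ECG heart-rate class would therefore not implement Appendix 8. That is a fair limit on what the class would mean, not a reason to report only the upper extreme.

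**Conclusion.** The point holds as a minor reporting gap. For ECG heart rate, part of a primary endpoint, no specified ECG table gives each participant's lowest rate, largest fall, or the number (%) with a low rate; for pulse rate the SAP provides a maximum decrease and a low-rate class. The practical effect is confined mainly to transient falls with recovery, since sustained falls show partly in the present extremes. Data and signal are retained elsewhere.

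The reversed subtraction in SAP 6.1.5 is a separate drafting fault in the same paragraph. The QTcF classes for increase from baseline make the intended direction clear, but the sentence contradicts it.

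This rests on three assumptions: the heart-rate series are illustrative; increase is read as postdose minus baseline except where the literal formula is tested; and the sponsor's reporting standards, which the SAP cites but does not reproduce, do not already supply the missing outputs.

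**What to change.** 1. In SAP 6.1.5 add, for heart rate, the minimum postdose value and the maximum decrease from baseline over all postdose ECGs, using the replicate mean where ECGs are triplicate.
2. In SAP Appendix 1 add an ECG heart-rate row with the reporting limits already set there for pulse rate (minimum <40, maximum >120 bpm), tabulated by treatment; or state in 6.1.5 that the pulse-rate classes serve this purpose. The row would be a reporting class only and would change no clinical rule.
3. Correct the ECG sentence so that change is postdose minus baseline, as for the increase in SAP 6.1.4.

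The cost is SAP wording and a small addition to existing tables. All the data are already collected, and no protocol change is needed.

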8.3.3. Electrocardiograms

Standard 12-lead ECGs utilizing limb leads (with a 10-second rhythm strip) should be collected at times specified in the SoA section of this protocol using an ECG machine that automatically calculates the HR and measures PR interval, QT interval, QTcF, and QRS complex. Alternative lead placement methodology using torso leads (eg, Mason-Likar) should not be used given the potential risk of discrepancies with ECGs acquired using standard limb lead placement. All scheduled ECGs should be performed after the participant has rested quietly for at least 5 minutes in a supine position.

Triplicate 12-lead ECGs will be obtained approximately 2 to 4 minutes apart at all time points during clinical confinement; the average of the triplicate ECG measurements collected

at each nominal time point on Day 1 will serve as each participant's time-controlled baseline OTcF value.

To ensure safety of the participants, a qualified individual at the investigator site will make comparisons to baseline measurements. Additional ECG monitoring will occur if a) the mean value from the triplicate measurements for any postdose QTcF interval is increased by ≥60 ms from the baseline and is >450 ms; or b) an absolute QT value is ≥500 ms for any scheduled ECG. If either of these conditions occurs, then a single ECG measurement must be repeated at least hourly until QTcF values from 2 successive ECGs fall below the threshold value that triggered the repeat measurement.

If a) a postdose QTcF interval remains ≥60 ms from the baseline and is >450 ms; or b) an absolute QT value is ≥500 ms for any scheduled ECG for greater than 4 hours (or sooner, at the discretion of the investigator); or c) QTcF value get progressively longer, the participant should undergo continuous ECG monitoring. A cardiologist should be consulted if QTcF values do not return to less than the criteria listed above after 8 hours of monitoring (or sooner, at the discretion of the investigator).

In some cases, it may be appropriate to repeat abnormal ECGs to rule out improper lead placement as contributing to the ECG abnormality. It is important that leads be placed in the same positions each time in order to achieve precise ECG recordings. If a machine-read QTc value is prolonged, as defined above, repeat measurements may not be necessary if a qualified medical provider's interpretation determines that the QTcF values are in the acceptable range.

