# Categories for PR and QRS

PR (ms)	max. ≥300	
PR (ms) increase from baseline	Baseline >200 and max. ≥25% increase	Baseline ≤200 and max. ≥50% increase
QRS (ms)	max. ≥140	
QRS (ms) increase from baseline	≥50% increase	

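### SAP 6.1.5 reverses the sign of the ECG increase from baseline, so the maximum increases and the QTcF, PR and QRS increase categories are wrong if programmed as written

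*SAP*

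**What the plan says.** For QTcF, QT, heart rate, PR and QRS, SAP 6.1.5 asks for the largest postdose value and the largest increase from baseline over all postdose measurements. It defines the increase thus: "The increase from baseline will be calculated by first subtracting each post-dose measurement from individual participant's baseline to give the change from baseline". Taken literally, this is baseline minus postdose.

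SAP 6.1.4, the section just before it, defines both directions for vital signs. For an increase: "The increase from baseline will be calculated by subtracting the baseline value from each postdose measurement". For a decrease: "decrease from baseline will be calculated by subtracting each post-dose measurement from individual participant's baseline value".

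The only other definition of ECG change in the SAP comes later in 6.1.5, under Safety QTcF Assessment: "the change between the postdose QTcF value and the average of the predose triplicate values on Day 1". Protocol 9.3.1.1 is worded the same way. Neither gives an order of subtraction.

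The increase feeds two sets of categories. For QTcF, the classes are 30-60 ms (moderate) and above 60 ms (severe). For the conduction intervals, "PR and QRS maximum values and maximum increases from baseline will also be tabulated by treatment". In Appendix 1, the row "PR (ms) increase from baseline" requires at least 25% if baseline exceeds 200 ms and at least 50% otherwise; QRS requires at least 50%.

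On the baseline itself, SAP 3.1.4 averages the three Day 1 predose triplicates. Protocol 8.3.3 instead says that the triplicate averages "at each nominal time point on Day 1 will serve as each participant's time-controlled baseline", without the word predose.

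**The concern.** Two adjacent SAP sections give opposite formulas for the same term, and the ECG formula nearly repeats the vital-signs formula for a decrease. It looks like a decrease rule pasted into the ECG section.

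SAP 3.1 makes ECG change from baseline a primary endpoint, and the QTcF increase classes are its categorical output. With the sign reversed, a table meant to show prolongation would show shortening. The absolute-value classes do not replace it, because a participant can rise by more than 60 ms and still end at or below 450 ms.

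Two smaller wording conflicts sit alongside. Protocol 8.3.3 drops predose from the QTcF baseline in the section that site staff use for the 60 ms monitoring comparison; the above-60 ms withdrawal rule in Protocol 7.1.2 also depends on baseline. SAP 6.1.4 limits the maximum vital-signs increase to the dosing period, while its own bullet covers all postdose measurements.

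**Working it through.** The plan states no figure that depends on this rule, so there is none to reproduce. The check applies both orders of subtraction to illustrative values and classifies the results with the plan's own cut-offs. The participant values are assumptions; the cut-offs come from SAP 6.1.5 and Appendix 1.

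**Formulas.** Let B be baseline and Y a postdose value.
- Intended: maximum increase = max(Y − B) = (highest Y) − B.
- As written: maximum increase = max(B − Y) = B − (lowest Y), which is the largest fall.

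**One postdose value per participant**

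| Parameter | B → Y (ms) | Intended | As written | Absolute-value category |
|---|---|---|---|---|
| QTcF | 400 → 465 | +65, severe | −65, none | 465: mild |
| QTcF | 465 → 400 | −65, none | +65, severe | 400: none |
| QTcF | 380 → 445 | +65, severe | −65, none | 445: none (not above 450) |
| PR | 160 → 240 | +80/160 = +50%, flagged | −50%, not flagged | 240: none (below 300) |
| PR | 160 → 80 | −50%, not flagged | +50%, flagged | 80: none |
| QRS | 90 → 135 | +45/90 = +50%, flagged | −50%, not flagged | 135: none (below 140) |

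**Several postdose values per participant**, which is how the maximum would be taken

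| QTcF baseline → postdose (ms) | Intended maximum increase | As written |
|---|---|---|
| 400 → 410, 465, 430 | max(10, 65, 30) = +65, severe | max(−10, −65, −30) = −10, none |
| 430 → 420, 365, 410 | max(−10, −65, −20) = −10, none | max(10, 65, 20) = +65, severe |
| 410 → 445, 400, 408 | max(35, −10, −2) = +35, moderate | max(−35, 10, 2) = +10, none |

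Lowering the first series by 20 ms gives 380 → 390, 445, 410. The intended result is still +65 and the as-written result still −10, but the highest value is now 445 ms, so the participant is in no QTcF category at all.

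As written, a participant is classified correctly only when the largest fall happens to land in the same class as the largest rise.

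**When the absolute classes cannot compensate.** To end at or below 450 ms after a rise of more than 60 ms, baseline must be below 450 − 60 = 390 ms. After a rise of exactly 30 ms, it must be at or below 450 − 30 = 420 ms.

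**Weight of one participant.** Protocol 4.1.1 and 4.1.2 plan 2, 2, 4 and 6 active participants in Cohorts 1 to 4 and 6 in Cohort 5. One misclassified active participant is 1/2 = 50% of the active arm in Cohorts 1 and 2, 1/4 = 25% in Cohort 3 and 1/6 = 17% in Cohorts 4 and 5.

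**The case against.** The strongest reply is that this is a slip whose meaning nobody would mistake. The result is called an increase and feeds a table of degrees of prolongation. SAP 6.1.4 has the right order, Protocol 9.3.1.1 lacks the faulty sentence, and SAP 2.1 declares no departure from the protocol's analysis. Harm needs a programmer to produce a prolongation table that counts shortening. The study is descriptive, and no escalation, withdrawal or monitoring rule uses this SAP sentence. If the by-time change summaries took the same sign, they could be recovered by flipping it.

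This shows that the reversal was unintended and limits its severity. It does not supply any text that overrides the sentence.

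Two points of detail also stand. With several postdose values, the as-written result for a participant with a +65 ms peak is −65 only if every value is at least 65 ms above baseline; the second table shows −10, but the severe case is still missed. And raw listings are unaffected, but Appendix 1 also calls for listing measurements that meet its criteria. If that note, placed after the vital-signs table, covers ECG too, that listing inherits the error.

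On the side points, Protocol 9.3.1.1, SAP 3.1.4 and the Schedule of Activities note all identify the Day 1 predose ECGs, so a postdose baseline is unlikely in practice. Single-dose participants also have no later dose to withhold. Both wording conflicts are real but rank well below the sign error.

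**Conclusion.** The concern holds: SAP 6.1.5 is wrong as written and should be fixed. Followed literally, it gives the wrong maximum increase for five ECG parameters and wrong increase categories for QTcF, PR and QRS, including cases where a rise above 60 ms appears in no QTcF category. Maximum absolute values, absolute-value categories and counts of QT above 500 ms are unaffected.

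The conclusion is conditional on literal programming. It assumes nothing about how often large changes occur, so the number of participants affected cannot be predicted. No hypothesis test, power or sample size is involved.

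**What to change.** In SAP 6.1.5, reverse the order: compute ECG change as each postdose value minus the participant's own baseline, and take the maximum increase as the largest of those differences. Giving the same order in the later QTcF definition would remove the remaining ambiguity.

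Secondary: in Protocol 8.3.3, state that the QTcF baseline is the average of the three predose triplicates on Day 1. Minor: in SAP 6.1.4, take the maximum vital-signs increase over all postdose measurements rather than over the dosing period.

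The cost is one reordered SAP sentence, plus a few words in the SAP and a non-substantial clarification in the protocol. Design, data collection and sample size do not change.
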